#### **Data Analysis**

Primary Outcome Analysis: The primary outcomes will be the number of participants screened, the prevalence of glaucoma/glaucoma suspect diagnosis and the cost per case of detected disease. related macular degeneration) will be summarized similarly. Based on the anticipated sample size (n=5800), the margin of error is at most 1.2 percentage points for the overall prevalence (but could be larger for annual and by-site estimates).

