has moderate or severe glaucoma, they can be referred to see the glaucoma specialist from UM who will have one day of clinic per month at Hamilton Clinic. If a patient from Hope requires further specialty consultation or surgery, they will sign up for MSupport, the UM charity care program, with the financial counselor available on-site during the Saturday clinics. Once a patient receives MSupport, they receive free care and medications at the UM for 12 months with the option to renew the services annually with proof of low income. Once a patient receives MSupport, they will be scheduled with the appropriate provider at the UM. For participants that are glaucoma/glaucoma suspect and seen at Hamilton or the Kellogg Eye Center for their follow up exam, these findings and visual field data will be collected and entered into the REDCap database.

One-Year Vision Outcomes: Repeat screenings at one year following the participants initial enrollment will take place during the second and third year of the program, where phone calls will be made to participants screened in the first or second year of the program (regardless if they screened positive or negative for disease) to encourage them to return for a second screening. When they return, they will follow the same protocol as described for the initial visits with the ophthalmic technician above. Although, One-Year visit survey data will only include demographics and the VFQ-9 and Falls survey which they also completed in their initial enrollment. Participants who were already randomized to the clinical trial in Aim 3 will not be re-randomized.

**Two-Year Vision Outcomes**: Repeat screenings will take place during the third year of the program, where phone calls will be made to all participants screened in the first year (regardless if they screened positive or negative for disease) to encourage them to return for a second screening. When they return, they will follow the same protocol as described for the initial visits with the ophthalmic technician above. Participants who were already randomized to the clinical trial in Aim 3 will not be re-randomized.

Participants that do not return to the clinic for a repeat screening examination, will be asked to complete the VFQ-9 survey over the phone when they are contacted.

One and Two-Year Vision Outcomes: These participants will need to meet the inclusion/exclusion criteria listed in section Recruitment Section of this protocol.

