**Post Program Participant Interview:** We will ask up to 75 participants to participate in a post program interview to identify program components that are helpful/unhelpful and areas for improvement. We will randomly contact English speaking participants within our study database that agreed to be contacted for future studies. The study consent document contains an additional signature section for participants to consent/not consent contact for future research. Selected participants will be contacted by phone, or in-person following their last appointment. Interviewers will follow the survey interview guide. Interviews will be conducted via in-person at the clinics, telephone, or UM Zoom. Participants will receive a \$20.00 Visa Gift Card or check by mail or in-person. Additionally, interviews will be recorded, transcribed, and stored on a secure UM server. Qualitative software such as Dedoose may be utilized. 1/24/2023 English post program interviews have been completed.

**Evaluation of "No-show" Appointments:** We will evaluate our high (approximately 35%) no-show and last-minute cancelations rates at this community clinic study (Hope & Hamilton

Community Clinic). The SIGHT study is open to non- clinic patients, therefore, potential participants may or may not be clinic patients. We will only review data of the SIGHT study "no shows" and will not include the clinics appointment "no shows". When potential participants contact the SIGHT team, the team member reviews the recruitment script that describes the study. Following this discussion and verification of study eligibility, a medical record number (MRN) in MiChart is created for those that do not already have an MRN. The SIGHT study baseline appointment is then made within the MiChart system. This process is completed prior to consent.

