#### **Outcomes**

Primary: The primary outcomes will be the number of participants screened and the prevalence of glaucoma/glaucoma suspect diagnosis and the cost per case of detected disease.

Secondary: 1a) Prevalence of other eye disease: visual impairment (visual acuity in the better seeing eye <20/40) on screening presentation, refractive error, cataract, diabetic retinopathy, and age-related macular degeneration. Prevalence will be determined by dividing the number of cases of disease on initial screening exam by the total number of participants who received screening each year. 1b) Incident disease will be estimated by

assessing the number of new cases of eye disease among the participants screened in the first year who returned for repeat screening in the third year. 2) The mean time since last eye exam: will be reported for the entire cohort of new patients seen for screening. The proportion of patients whose last eye exam was >2 years prior will be calculated for the cohort. 3) Vision related quality of life (NEI VFQ 9) will be assessed for all participants. The associations of vision related quality of life with eye disease diagnosis and demographic variables will be assessed. The 2-year change in vision and vision related quality of life will be measured for all participants screened in the first year of the program and re-screened in Year 3.

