Sample Size: Approximately 5,000 patients access the Hope Clinic per year and 25,000 patients access the Hamilton clinic per year. One technician will be assigned full-time to Hamilton. The other technician will split time between Hope (60%, Tuesday, Wednesday, Thursday) and Hamilton (40%, Monday and Friday) because there is such a higher volume of patients to screen at Hamilton and the Hope Clinic is not open on Mondays or Fridays. The clinic equipment at Hamilton will be set up to be used by both technicians. A typical day for each technician will include 5 screenings and 5 one-month follow-up visits. In the first 2 years (48 weeks each) at each site, all screenings will be of new or 1 year follow up patients. In the 3rd year, 2 will be new and 3 will be one or two-year re-screening visits. At Hope, the technician has capacity for 2448 new screenings and 432 repeat screenings in 4 years. At Hamilton, the technicians have capacity for 4872 new screenings and 1008 rescreenings in 3.5 years. Thus full capacity is 7320 new screenings and 1440 re-screenings. Operating at just 80% capacity enrolls over 5,800 patients for new screenings including over 1100 with 2-year re-screenings to determine impact on longer term visual acuity and visual function.

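### At n=5,800 the worst-case margin of error for overall prevalence is 1.29 points at an assumed 95% level, not at most 1.2 (minor correction)

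*Protocol*

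**What the plan says.** The Aim 2 Data Analysis section (Primary Outcome Analysis) gives one precision figure for the prevalence of glaucoma or glaucoma suspect: "Based on the anticipated sample size (n=5800), the margin of error is at most 1.2 percentage points for the overall prevalence". It adds that the margin "could be larger for annual and by-site estimates", so the ceiling applies to the overall estimate only.

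The sample size comes from the Sample Size paragraph of Aim 2, which multiplies out technician capacity: "Operating at just 80% capacity enrolls over 5,800 patients for new screenings".

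The visible text gives no confidence level, assumed prevalence, interval method or finite-population correction for the figure. The sentence just before it is broken, so some wording on how prevalence will be summarised appears to be missing.

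**The concern.** A margin of error described as a maximum, with no prevalence attached, is normally read as the value at a prevalence of 50%, where the binomial variance is largest. At 95% confidence and n=5,800 that value is nearer 1.3 than 1.2, so the stated ceiling is too low and errs in the favourable direction.

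Little is at stake. This is the only precision statement visible for a primary outcome, and a reader can check it in one line. It feeds no test, power calculation or stopping rule.

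**Working it through.** **Inputs**
- n = 5,800 (Aim 2, Data Analysis).
- Basis of n: 80% of 7,320 new screenings = 5,856 (Aim 2, Sample Size).
- Confidence level: not visible. 95% two-sided is assumed; 90% and 99% are also tried.
- Prevalence: not stated for this figure. A maximum implies p = 0.5.
- Background rates for glaucoma plus suspect: 17% + 21% = 38% (Philadelphia) and 19% + 23% = 42% (Birmingham). Adding them assumes that the two categories do not overlap.

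**Formula:** margin in points = 100 × z × sqrt(p(1−p)/n).

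**Attempt to reproduce 1.2**

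| Setting | Margin (points) |
|---|---|
| 95%, p=0.5, n=5,800: 100 × 1.96 × sqrt(0.25/5,800) | 1.287 |
| Same, n=5,856 | 1.281 |
| Same, Wilson interval, n=5,800 | 1.286 |
| Same, exact (Clopper-Pearson) interval, n=5,800 | 1.295 |
| 90%, p=0.5, n=5,800 | 1.080 |
| 99%, p=0.5, n=5,800 | 1.691 |
| 95%, p=0.42, n=5,800 | 1.270 |
| 95%, p=0.38, n=5,800 | 1.249 |
| 95%, p=0.32, n=5,800 | 1.201 |

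No 95% worst-case variant gives 1.2. The interval method and the exact n move the result only in the second decimal, and 1.287 rounds to 1.3. At p=0.5 a margin of 1.2 means z = 0.012/sqrt(0.25/5,800) = 1.828, a confidence level of 93.2%, which is not a conventional choice.

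**Where 1.2 is a valid 95% bound.** Solve p(1−p) = 5,800 × (0.012/1.96)² = 0.2174. This gives p = 0.319, or 0.681 on the other side. The ceiling therefore holds for prevalence up to about 32% (or of about 68% and above). If the margin is rounded to one decimal, so that anything up to 1.25 counts as 1.2, it holds up to about 38%.

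**Finite-population correction.** The Sample Size paragraph says: "Approximately 5,000 patients access the Hope Clinic per year and 25,000 patients access the Hamilton clinic per year". With N = 5,000 + 25,000 = 30,000 the factor is sqrt((30,000 − 5,800)/29,999) = 0.898, and 1.287 × 0.898 = 1.156. This would bring the figure under 1.2, but the visible text mentions no correction and N is a yearly access count, while screening runs over about four years. The paragraph on no-show appointments also says: "The SIGHT study is open to non- clinic patients". With N = 60,000, taken only as an illustration, the margin is 1.223.

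**The case against.** The best defence is that the check supplies an input that the protocol does not show. The text is visibly damaged just where a level or an assumed prevalence would normally stand, and a level could also be in a statistical analysis plan that is not at hand. At 90% the ceiling of 1.2 is true. This stands in part: the result depends on the 95% assumption and must be reported that way.

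A second defence is that the ceiling may be meant over the plausible range of prevalence only. Taken separately, the Background rates (17% to 23%) give at most 1.08, and the combined 38% gives 1.249, which rounds to 1.2. But the primary outcome combines glaucoma and suspect, and the other combined rate cited, 42%, gives 1.27. This reading therefore does not cover all of the protocol's own background figures, and a bound of that kind would need its range stated.

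A third defence is that the difference is trivial. That is correct, and it limits the point to a minor correction.

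A reader might infer more than the document supports in two ways:
- **That the study is too small.** A true 95% ceiling of 1.2 would need 1.96² × 0.25/0.012² = 6,670 new screenings, or 6,670/7,320 = 91% of capacity. But n was derived from technician capacity, and nothing makes 1.2 points a target.
- **That annual prevalence in secondary outcome 1a is diluted by repeat visits.** It is obtained by "dividing the number of cases of disease on initial screening exam by the total number of participants who received screening each year", while outcome 2 names new patients explicitly. But outcome 1a is anchored to the first exam, repeat screening is handled in outcomes 1b and 3, and the Sample Size paragraph counts new and repeat screenings separately. On the sensible reading, first exams over first-screened participants, there is no bias. The overall prevalence is unaffected either way. At most this is a clarification that a statistical analysis plan would commonly give.

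**Conclusion.** The point holds as a minor correction of one stated number. Assuming 95% confidence, the largest margin of error at n=5,800 is 1.29 points, 0.09 above the stated ceiling, and the ceiling is also exceeded at both combined background rates (1.25 and 1.27). The readings that would justify 1.2 are a 90% level, a finite-population correction with N=30,000, or a prevalence of no more than about 32%. None is stated for this figure.

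The conclusion rests on the 95% assumption and on taking the ceiling as a maximum over all prevalences. It says nothing against the sample size, the overall prevalence estimate or the definition of the secondary outcomes.

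**What to change.** In the Aim 2 Data Analysis section, give the maximum margin for overall prevalence as 1.3 percentage points and name the 95% confidence level.

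If 1.2 was derived at another confidence level, for an assumed prevalence, or with a finite-population correction, keep it but state that assumption, and do not present it as a maximum beyond it.

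The cost is one phrase. No new data, change of sample size or change of analysis is needed; the stated precision becomes slightly less favourable.

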# Aim 3: Integrate personalized glaucoma education and counseling during the technician visitand test the behavior intervention's impact on adherence to follow-up care with an ophthalmologist.

#### Overall strategy and experimental rigor.

In Aim 3, we will refine and optimize our eHealth-based, personalized education and counseling intervention that improves glaucoma medication adherence to also help support people in prioritizing returning for glaucoma care. This intervention uses a web-based application to generate personalized education materials for patients based on their diagnosis, test results, doctor's recommendations, and barriers to following those recommendations. A glaucoma counselor trained in brief, glaucoma-specific motivational interviewing (MI) uses the

individualized content generated from this web-based application to form the basis of her conversation with the patient. The glaucoma counselor uses MI-based communication strategies – including open-ended questions, reflective listening, and asking permission to give advice – to engage the person in identifying their own barriers to participating in glaucoma follow-up care and brainstorming their own solutions. All patients who screen positive for a diagnosis of glaucoma or glaucoma suspect and are being referred for an in-person examination with an ophthalmologist and who speak English will be randomized to receive either A) a 30-minute session with help scheduling the follow up appointment with an ophthalmologist and an educational hand-out or B) a 60-minute session with help scheduling the follow-up appointment with an ophthalmologist and a personalized counseling and education session about glaucoma. Spanish speaking participants will not be randomized and will receive personalized counseling and education about glaucoma. As of March 2024, Spanish speaking participants will be asked to choose eHealth education or standard education.

# Rationale for experimental design.

Both empowerment theory and self-determination theory form the basis for our health and counseling intervention. The World Health Organization describes empowerment as a "process through which people gain greater control over decisions and actions affecting their health." Empowerment is particularly important for people who may experience a powerlessness that can come with minority status or poverty. To empower people to best manage their eye health, people must be supported to develop knowledge and skills about their health condition, coping skills for managing emotions that can negatively affect self-management, and motivation to attain improved health. Self-determination theory posits that to change a health behavior, people must feel autonomously supported and connected to their health care provider, perceive that they are competent to engage in the behavior, and be motivated to change their behavior.

Thus, the two theories provide very similar frameworks for understanding how to help people improve their health behaviors. MI is a counseling style consistent with the frameworks of self-determination theory and empowerment theory. This counseling engages patients by discussing priorities and obstacles to facilitate intrinsic motivation to change health behavior. At its base is a belief that an individual must develop a personally compelling reason to motivate a change in behavior for that change to happen.

## **Research design-Intervention**

Block randomization: Subjects will be randomized to one of two treatment arms (standard glaucoma education from handouts or personalized education with counseling) in a 1:1 ratio. The time of randomization is when the patient returns for their follow-up visit with the ophthalmic technician. Randomization will occur separately for the two clinics (stratification). A variable-block randomization scheme will be used to assure balanced assignment to the treatment arms throughout the study.

Leveraging eHealth to provide personalized glaucoma education and counseling: The web-based application for personalized glaucoma education has two components woven together into a single tool to support the conversation between the patient and the glaucoma

counselor: 1) an electronic health (eHealth) component and 2) a semi-structured, tailored interview guide to facilitate an MI-based conversation. The eHealth component provides individually tailored disease information and an explanation of a patient's test results. The counselor uses the web-based application on a tablet, to share engaging audio-visual content on a screen. The counselor walks a patient through their diagnosis and test results and what would happen to their vision if glaucoma goes untreated. The counselor then elicits an understanding of what motivates that patient to maintain their vision. The counselor explores what unique obstacles the patient has to engaging in follow-up care. The counselor then assesses the patient's motivation to attend the follow-up appointment. The counselor and patient create a concrete "action plan" that delineates the short-term plan of the steps patient will take to address any identified barriers to follow-up care, which can include addressing motivational factors in a subsequent phone visit if a patient is not interested in follow-up care.

Throughout the program, the counselor helps patients put together a list of questions for their doctor to prepare for their visit. African-American patients are often less active in asking questions of health care providers,  so supporting question-asking during medical visits is a key modifiable patient engagement behavior. Creating a question prompt list for patients can improve patients' information recall after the doctor visit, reduces patients' anxiety about the visit, and improves self-efficacy for question-asking.  At the end of the visit, the counselor will print out a patient's action plan with their appointment time for the ophthalmologist, the list of questions to bring to the appointment, and login information in case the patient would like to access the website to view their education plan remotely.

Between 2-6 weeks after the counseling session, depending on when the glaucoma follow-up appointment is scheduled, the ophthalmic technician will make at least 3 attempts to contact within a 30 day window to schedule a phone call with the patient. During this phone call, the technician will remind the patient of when their upcoming appointment is scheduled. S/he will assess a patient's motivation and confidence in attending the visit and elicit possible obstacles. S/he will help the patient brainstorm possible solutions to identified obstacles and end the conversation by summarizing a new action plan. If needed, the counselor can arrange a subsequent phone call before the follow-up appointment to checkin about any outstanding problems. Patients will have the counselor's phone number to call if they need additional help.

Training para-professional staff in brief, glaucoma-specific motivational interviewing: We have developed a 2- day training program in brief, glaucoma-specific MI.  The program focuses on teaching the five core skills of MI: 1) asking open-ended questions; 2) affirming; 3) reflecting; 4) summarizing; 5) asking permission to provide information and advice.  These skills help elicit "change talk," through which counselors help patients talk themselves into changing their usual behavior, which in this case will be to ensure they attend their glaucoma follow-up care appointment. The program also teaches the counselor how to express empathy, with is the key component that underlies the spirit of MI and promotes rapport between the counselor and the patient.

During the first day of training, counselors are taught to ask open-ended questions, or questions that cannot be answered with a "yes" or "no" response. They learn reflective listening, or para-phrasing what a person has said to ensure the person knows the counselor

is hearing and understanding what they say. They learn to use affirmations to praise actions people are taking towards improving their health and vision. They learn to use the elicit-provide-elicit technique to give information. This involves assessing people's knowledge prior to giving information, asking permission to give new information or advice, and then following up by eliciting the person's response to the new information in order to evaluate their understanding. This non-directive way of giving advice and information supports people's autonomy. During the second day of training, counselors are taught how to make complex reflections.

Complex reflections are statements that para-phrase what a person has said and adds significant meaning to help make a person think about the implications of their statement. Counselors learn how to promote change talk and develop an action plan to adhere to follow-up care recommendations.

Role playing is used to develop these skills using a video collection of glaucoma patients explaining their reasons for not engaging in their glaucoma management. The training consists of approximately 35% didactic material and 65% role-playing and interactive learning.

Primary outcome: The primary outcome will be adherence to the recommended follow-up appointment with the ophthalmologist within 6 months due to availability in scheduling these appointments. Six-month adherence will be used as the endpoint for all participants. Adherence in each treatment group will be calculated as the proportion of patients who attended the initial scheduled follow-up visit with an ophthalmologist as recommended after being diagnosed with glaucoma or glaucoma suspect on screening exam, dividing by the total number of patients diagnosed with glaucoma or glaucoma suspect during the screening exam and scheduled for follow-up with an ophthalmologist. This objective outcome variable will be assessed through record review by the study coordinator who is masked to the treatment allocation.

Maintaining Fidelity to Treatment Allocation: All counseling/education encounters will be audio-recorded. A study therapist and MI trainer, will assess a random sample of 10% of encounters (n=40) for fidelity to MI-based counseling. She will be masked to treatment allocation though the personalized counseling sessions will be longer than standard education. She will assess each encounter according to the modified One Pass grading system, a rubric with 17 items that assesses fidelity to MI counseling techniques. Each item is scored on a Likert scale from 1 to 7 and a passing score is set at a mean of 5. Counselors should not be using motivational interviewing-based counseling in the control group and therefore should have an average One Pass score <5 for these participants.

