Aim 3: (Phase 2- HUM 00169371) Integrate personalized glaucoma education and counseling during the technician visit and test the behavioral intervention's impact on adherence to follow-up care with an ophthalmologist. We hypothesize that personalized eHealth education and motivational-interviewing-based counseling will improve adherence to glaucoma follow-up care compared to standard education delivered by a trained staff member. We will test our hypothesis in a randomized controlled trial with participants (n=400) from Aim 2 who have glaucoma or suspected glaucoma. We will make iterative refinements to our existing evidence-based, individualized counseling/eHealth glaucoma education program with a focus on adherence to follow-up recommendations based on learning in Aim 1. The primary outcome is the proportion of participants attending the recommended physician appointments within three months. Secondary outcomes include glaucoma knowledge, satisfaction with communication, and confidence in asking the ophthalmologist questions. Program economic efficiency will be assessed.

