# **Data Analysis**

Primary outcome: The primary outcome (attendance to follow-up appointment with a glaucoma specialist within three months) will be summarized with frequencies and percentages by intervention and control groups, overall and stratified by site.

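### The Aim 3 primary outcome is follow-up within six months, but its scoring rule counts only the initial scheduled visit, so a participant who rebooks and is seen in time can be scored non-adherent

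*Protocol*

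**What the plan says.** The primary outcome paragraph under *Research design-Intervention* (Aim 3) states the outcome in words: "The primary outcome will be adherence to the recommended follow-up appointment with the ophthalmologist within 6 months due to availability in scheduling these appointments". It adds: "Six-month adherence will be used as the endpoint for all participants". Neither sentence requires that the visit be the first one booked.

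The calculation follows: "Adherence in each treatment group will be calculated as the proportion of patients who attended the initial scheduled follow-up visit with an ophthalmologist". The denominator is formed by "dividing by the total number of patients diagnosed with glaucoma or glaucoma suspect during the screening exam and scheduled for follow-up with an ophthalmologist".

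Two other places describe the same outcome without a first-booking condition. The Aim 3 summary under *Specific Aim/Hypothesis* says: "The primary outcome is the proportion of participants attending the recommended physician appointments within three months". The Aim 3 *Data Analysis* section has "attendance to follow-up appointment with a glaucoma specialist within three months". (Their three-month limit conflicts with six months. That is a separate matter and is not relied on here.)

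The protocol nowhere says how to score a visit that is rescheduled by the patient, moved by the clinic, or missed and later made up.

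**The concern.** The paragraph states one quantity and calculates another. The outcome in words is whether the patient reached an ophthalmologist within six months. The numerator, read literally, is whether the patient kept the first appointment made. The two differ for everyone who is seen in the window on a later date.

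Such patients are to be expected. The protocol reports "high (approximately 35%) no-show and last-minute cancelations rates" for the study's own appointments. The Hope-Kellogg ophthalmology clinic runs on one Saturday every two months, so a patient who cannot make one session may be seen at the next and still fall inside six months.

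Two things are at stake. Adherence is understated in any arm where someone rebooks and attends. The contrast between arms also depends on a definition the text leaves unsettled: the coordinator scores from record review, and two careful people could score the same rebooked patient differently. This matters more because, under *Planned Analysis Results Nov. 14, 2023*, a planned analysis found no difference in adherence and randomisation was then stopped. The protocol does not say which scoring produced that result.

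**Working it through.** The protocol gives no power, control rate or target effect for Aim 3, so there is no stated figure to reproduce. The check compares the two scoring rules.

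**Inputs**
- Arm size: n=400 randomised 1:1 (protocol), so 200 per arm if the planned number was reached.
- First-booking attendance in controls: 65%. Assumed, as 100% − 35%. The 35% is for study appointments, not the ophthalmologist visit, so it is only a proxy.
- First-booking attendance in the coached arm: 65% or 75%. Assumed.
- Share of those missing the first booking who are seen later within six months: 20% to 50%. Assumed; the documents give no rebooking rate.

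**Formulas**

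Let p be first-booking attendance and r the share of missers seen later in the window (C = control, I = coached).
- First-booking rule: p
- Any visit within six months: p + (1 − p)r
- Understatement within an arm: (1 − p)r
- Any-visit difference minus first-booking difference: (1 − pI)rI − (1 − pC)rC

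**Level of adherence.** With p = 0.65, the understatement is 0.35 × 0.20 = 7.0 points, or 0.35 × 0.50 = 17.5 points.

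**Difference between arms**

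| First booking, C v I | Rebooked and seen, C v I | First-booking difference | Any-visit rates, C v I | Any-visit difference |
|---|---|---|---|---|
| 65% v 65% | 20% v 50% | 0 | 72.0% v 82.5% | 10.5 |
| 65% v 65% | 30% v 50% | 0 | 75.5% v 82.5% | 7.0 |
| 65% v 75% | 20% v 40% | 10.0 | 72.0% v 85.0% | 13.0 |
| 65% v 75% | 20% v 20% | 10.0 | 72.0% v 80.0% | 8.0 |
| 65% v 75% | 50% v 50% | 10.0 | 82.5% v 87.5% | 5.0 |
| 65% v 75% | 50% v 30% | 10.0 | 82.5% v 82.5% | 0 |

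Example, first row: 0.65 + 0.35 × 0.20 = 0.720; 0.65 + 0.35 × 0.50 = 0.825; difference 0.105.

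With equal rebooking r in both arms, the any-visit difference is the first-booking difference times (1 − r): 10 × 0.8 = 8 and 10 × 0.5 = 5. With first-booking attendance of 65% v 75%, any-visit scoring widens the gap only if 0.25 rI > 0.35 rC, that is, if coached missers rebook and attend at more than 1.4 times the control rate.

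**What this means for power.** With 200 per arm and an assumed two-sided 5% test of two proportions (normal approximation), power is 0.71 for 72.0% v 82.5%, 0.59 for 65% v 75%, 0.47 for 72.0% v 80.0% and 0.29 for 82.5% v 87.5%. The choice of rule can therefore change what the trial is able to detect, in either direction.

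**The case against.** **The wording has a benign reading.** *Initial* may mean the first ophthalmology visit after screening, as opposed to later ones, whenever it takes place. That fits the two sentences before it, the stated reason for six months, and the other two descriptions of the outcome. This stands as a possibility, so it is not certain that rebooked patients were scored non-adherent. It does not rescue the text: it leaves the word *scheduled* with little to do, and no rule on rebooking is given. An unseen analysis plan might supply one, but the protocol itself fixes the numerator and should agree with its own outcome.

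**No bias against coaching is shown.** A reader might infer that the rule hides the coaching effect and pushed the trial towards its null result. The documents do not support that. An illustration with 65% first-booking attendance in both arms gets its zero by assuming that coaching does nothing for the visit it most directly targets. The coaching call reminds the patient of the booked appointment. It is also meant to "help the patient brainstorm possible solutions to identified obstacles and end the conversation by summarizing a new action plan", which may lead to rebooking, but rescheduling is not mentioned. Both arms receive scheduling help and a reminder call. With equal rebooking, the first-booking rule shows the larger difference. This objection stands in full.

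**The six-month window still does some work.** Even on the literal reading it decides whether a late first slot counts. This also stands, so the window is not redundant.

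**Changing a primary numerator after a null result is hazardous.** Agreed. The fix must preserve the reported result and label any added scoring.

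**Conclusion.** The point holds as an inconsistency in the primary outcome definition, not as a demonstrated bias. The outcome in words is follow-up within six months; the calculation, read literally, is attendance at the first booking.

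On that literal reading, adherence is understated in any arm where someone rebooks and attends. The size is 7.0 to 17.5 points under the assumed 65% first-booking attendance and 20% to 50% rebooking. The effect on the difference between arms can go either way, and neither its direction nor its size can be determined from the documents, because no first-booking or rebooking rates are given by arm. Nothing here shows that the November 2023 finding of no difference is wrong. It shows that a reader cannot tell which quantity that finding refers to.

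**What to change.** Reword the numerator under *Research design-Intervention* to count attendance at any ophthalmologist follow-up visit for the glaucoma or glaucoma-suspect referral within the six-month window, at the first or a rebooked date. Report attendance at the first booking as a secondary measure.

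State which rule the November 2023 analysis used. If it already counted any visit in the window, the wording change is enough. If it used the first-booking rule, keep that result as reported and present the any-visit scoring beside it, labelled as specified after that result was known.

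The cost is a wording amendment and some re-scoring from existing records. Adherence is already followed through record review and weekly electronic health record reports, so no new visits are needed. The protocol does not say whether rebooked dates were entered in the research database, so some may have to be looked up again. The added analysis may carry a post hoc label.
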